10.5 Analysis Time Points

10.5.1 Final Analysis

The final analysis of the study will occur when all patients have had the opportunity to be observed for at least 6 months for ORR and PFS.

10.5.2 Planned Interim Analysis

An interim analysis will be conducted after all patients in Part A have completed 2 tumor assessments or have discontinued from treatment. The tumor assessment period may be extended if emerging data show responses are occurring later, or if the tumor assessment for the final evaluated subject is delayed. Results from Part A will be used to inform the selection of biomarker-defined subgroups in Part B.

10.5.3 Efficacy Review

No formal efficacy review planned. However, results from Part A will be used to inform the selection of biomarker-defined subgroups in Part B.

10.5.4 Pharmacokinetic and Anti-Drug Antibody Analysis

Plasma concentration-time data will be listed, plotted, and summarized using descriptive statistics at each time point.

PK parameters will be listed and summarized using descriptive statistics.

The number and percentage of subjects who have a positive ADA result will be summarized with regards to: baseline prevalence of ADA (prior to first dose administration) – if applicable, post-baseline incidence of ADA (both total and in subjects with positive result at baseline), treatment-emergent incidence of ADA (positive post-baseline result where baseline result was negative or missing or ADA titer increased following positive baseline result).

CONFIDENTIAL

11. SAFETY REPORTING AND ANALYSES

Safety assessments will consist of monitoring and recording protocol-defined AEs and SAEs; measurement of protocol-specified hematology and clinical chemistry laboratory findings, vital signs; and other protocol-specified tests that are deemed critical to the safety evaluation of the study drug.

The Principal Investigator is responsible for recognizing and reporting SAEs to the Development Innovations Safety Department (see Section 11.1.5). It is Development Innovations' responsibility to report relevant SAEs to the applicable local, national, or international regulatory bodies. In addition, Investigators must report SAEs and follow-up information to their responsible IRBs according to the policies of each IRB.

The Principal Investigator is also responsible for ensuring that every staff member involved in the study is familiar with the content of this section.

11.1 Definitions

11.1.1 Adverse Events

Adverse event means any untoward medical occurrence associated with the use of a drug in humans, whether or not considered drug-related. An AE can be any unfavorable and unintended sign (e.g., an abnormal laboratory finding), symptom, or disease temporarily associated with the use of a drug, without any judgment about causality. An AE can arise with any use of the drug (e.g., off-label use, use in combination with another drug) and with any route of administration, formulation, or dose, including overdose.

11.1.2 Serious Adverse Event

An AE or a suspected adverse reaction (SAR) is considered “serious” if it results in any of the following outcomes:

- Death
- A life-threatening AE
- Inpatient hospitalization of at least 24 hours or prolongation of existing hospitalization
- A persistent or significant incapacity or substantial disruption of the ability to conduct normal life functions
- A congenital anomaly/birth defect

Important medical events that may not result in death, be life-threatening, or require hospitalization may be considered serious when, based upon appropriate medical judgment, they may jeopardize the patient and may require medical or surgical intervention to prevent one of the outcomes listed in this definition. Examples of such medical events include allergic bronchospasm requiring intensive treatment in an emergency room or at home, blood dyscrasias or convulsions that do not result in hospitalization, or development of drug dependency or drug abuse.

It is important to distinguish between “serious” and “severe” AEs, as the terms are not synonymous. Severity is a measure of intensity; however, an AE of severe intensity need not necessarily be considered “serious.” Seriousness serves as the guide for defining regulatory reporting obligations and is based on a patient/event outcome or an action usually associated

CONFIDENTIAL

with events that pose a threat to a patient's life or vital functions. For example, nausea that persists for several hours may be considered "severe" nausea but may not be considered an SAE. On the other hand, a stroke that results in only a limited degree of disability may be considered only a mild stroke but would be considered an SAE. "Severity" and "seriousness" should be independently assessed when recording AEs on the eCRF and SAEs on the SAE Report Form.

11.1.3 Adverse Reaction

An adverse reaction (AR) means any AE caused by a drug. Adverse reactions are a subset of all SARs where there is a reason to conclude that the drug caused the event.

11.1.4 Suspected Adverse Reaction

Suspected adverse reaction (SAR) means any AE for which there is a reasonable possibility that the drug caused the AE. "Reasonable possibility" means that there is evidence to suggest a causal relationship between the drug and the AE. An SAR implies a lesser degree of certainty about causality than AR, which means any AE caused by a drug.

11.1.5 Recording and Reporting of Adverse Events

Recording of Adverse Events

All AEs of any patient during the course of the research study will be recorded in the eCRF, and the Investigator will give his or her opinion as to the relationship of the AE to the study drug treatment (i.e., whether the event is related or unrelated to study drug administration).

All AEs should be documented. A description of the event, including its date of onset and resolution, whether it constitutes an SAE or not, any action taken (e.g., changes to study treatment), and outcome, should be provided, along with the Investigator's assessment of causality (i.e., the relationship to the study treatment[s]). For an AE to be a suspected treatment-related event, there should be at least a reasonable possibility of a causal relationship between the protocol treatment and the AE. Adverse events will be graded according to the NCI CTCAE Version 5.0, and changes will be documented.

If the AE is serious, it should be reported immediately to Development Innovations Safety Department. Other untoward events occurring in the framework of a clinical study are to be recorded as AEs (i.e., AEs that occur prior to assignment of study treatment that are related to a protocol-mandated intervention, including invasive procedures such as biopsies, medication washout, or no treatment run-in).

Any clinically significant signs and symptoms, abnormal test findings, changes in physical examination, hypersensitivity, and other measurements that occur will be reported as AEs and collected on the relevant eCRF screen.

Test findings will be reported as an AE if: the test result requires an adjustment in the study drug(s) or discontinuation of treatment and/or test findings require additional testing or surgical intervention, a test result or finding is associated with accompanying symptoms, or a test result is considered to be an AE by the Investigator.

Reporting Period for Adverse Events

All AEs, regardless of seriousness or relationship to patritumab deruxtecan treatment (called study treatment), spanning from the start of study treatment until 40 calendar days (+7 days) after discontinuation or completion of study treatment as defined by the clinical study for that patient

CONFIDENTIAL

after his/her last dose of study drug, are to be recorded on the corresponding screen(s) included in the eCRF.

All AEs resulting in discontinuation from the study should be followed until resolution or stabilization. All new AEs occurring during this period must be reported and followed until resolution unless, in the opinion of the Investigator, the AE or laboratory abnormality/ies is/are not likely to improve because of the underlying disease. In this case, the Investigator must record his or her reasoning for this decision in the patient's medical record.

After 40 days after completion of protocol-specific treatment or discontinuation, only AEs, SAEs, or deaths assessed by the Investigator as treatment-related are to be reported.

11.1.6 Assessment of Adverse Events

All AEs and SAEs, whether volunteered by the patient, discovered by study personnel during questioning, or detected through physical examination, laboratory tests, or other means, will be reported appropriately. Each reported AE or SAE will be described by its duration (i.e., start and end dates), regulatory seriousness criteria if applicable, suspected relationship to the study drug (see following guidance), and actions taken.

To ensure consistency of AE and SAE causality assessments, Investigators should apply the following general guideline:

YES: There is a plausible temporal relationship between the onset of the AE and administration of the study treatment, and the AE cannot be readily explained by the patient's clinical state, intercurrent illness, or concomitant therapies; and/or the AE follows a known pattern of response to the study drug; and/or the AE abates or resolves upon discontinuation of the study drug or dose reduction and, if applicable, reappears upon re-challenge.

NO: Evidence exists that the AE has an etiology other than the study drug (e.g., pre-existing medical condition, underlying disease, intercurrent illness, or concomitant medication), and/or the AE has no plausible temporal relationship to study drug administration (e.g., cancer diagnosed 2 days after first dose of study drug).

11.2 Serious Adverse Event Reporting by Investigators

Adverse events classified by the treating Investigator as "serious" require expeditious handling and reporting to the Development Innovations Safety Department in order to comply with regulatory requirements. Determination of "life-threatening" or "serious" is based on the opinion of either the Sponsor or the Investigator.

Serious AEs may occur at any time from the start of study treatment through the 40-day follow-up period after the last study treatment. **The Development Innovations Safety Department must be notified of all SAEs, regardless of causality, within 24 hours of the first knowledge of the event by the treating physician or research personnel.**

To report an SAE, the SAE Report Form should be completed with the necessary information.

The SAE Report Form should be sent to the Development Innovations Safety Department via fax or e-mail using the following contact information (during both business and non-business hours):

Sarah Cannon Development Innovations Safety Department

CONFIDENTIAL

Safety Dept. [contact]

Safety Dept. Email: [contact]

Transmission of the SAE report should be confirmed by the site personnel submitting the report.

Follow-up information for SAEs and information on non-serious AEs that become serious should also be reported to the Development Innovations Safety Department as soon as it is available; these reports should also be submitted using the Development Innovations SAE Report Form.

11.2.1 Investigator Reporting After Study Discontinuation

Forty days after completing protocol-specific treatment or study discontinuation, treatment-related AEs, SAEs, or deaths determined by the Investigator as treatment-related are to be reported directly to the Sponsor (Development Innovations).

11.3 Recording of Adverse Events and Serious Adverse Events

11.3.1 Diagnosis versus Signs and Symptoms

All AEs should be recorded individually in the patient's own words (verbatim) unless, in the opinion of the Principal Investigator or designated physician, the AEs constitute components of a recognized condition, disease, or syndrome. In the latter case, the condition, disease, or syndrome should be named rather than each individual sign or symptom. If a constellation of signs and/or symptoms cannot be medically characterized as a single diagnosis or syndrome at the time of reporting, each individual event should be recorded as an AE or SAE as appropriate on the relevant form(s) (SAE Report Form and/or AE eCRF). If a diagnosis is subsequently established, it should be reported as follow-up information is available. If a diagnosis is determined subsequent to the reporting of the constellation of symptoms, the signs/symptoms should be updated to reflect the diagnosis.

Progression of malignancy (including fatal outcomes), if documented by use of an appropriate method (e.g., as per RECIST criteria for solid tumors; see Appendix B), should not be reported as an SAE.

11.3.2 Persistent or Recurrent Adverse Events

A persistent AE is one that extends continuously, without resolution, between patient evaluation time points. Such events should be recorded only once on the SAE Report Form and/or the AE eCRF. If a persistent AE becomes more severe or lessens in severity, it should be recorded on a separate SAE Report Form and/or AE eCRF.

A recurrent AE is one that occurs and resolves between patient evaluation time points and subsequently recurs. All recurrent AEs should be recorded on an SAE Report Form and/or AE eCRF.

11.3.3 Abnormal Laboratory Values

If an abnormal laboratory value or vital sign is associated with clinical signs and/or symptoms, the sign or symptom should be reported as an AE or SAE, and the associated laboratory value or vital sign should be considered additional information that must be collected on the relevant eCRF. If the laboratory abnormality is a sign of a disease or syndrome, only the diagnosis needs to be recorded on the SAE Report Form and/or AE eCRF.

CONFIDENTIAL

Abnormal laboratory values will be reported as an AE if the laboratory result requires an adjustment in the study drug(s) or discontinuation of treatment, and/or laboratory findings require additional testing or surgical intervention, a laboratory result or finding is associated with accompanying symptoms, or a laboratory result is considered to be an AE by the Investigator.

11.3.4 Deaths

Deaths that occur during the protocol-specified AE reporting period that are attributed by the Investigator solely to progression of disease will be recorded on the “End of Study” eCRF. All other on-study deaths, regardless of attribution, will be recorded on an SAE Report Form and expeditiously reported to the Development Innovations Safety Department.

When recording a SAE with an outcome of death, the event or condition that caused or contributed to the fatal outcome should be recorded as the single medical concept on the SAE Report Form and Adverse Event eCRF. If the cause of death is unknown and cannot be ascertained at the time of reporting, record “Death NOS” (“death, cause unknown”) on the AE eCRF. During post-study survival follow-up, deaths attributed to progression of disease will be recorded on the “Follow-up Summary” and “Death Page” eCRFs.

11.3.5 Hospitalization, Prolonged Hospitalization, or Surgery

Any AE that results in a hospitalization of >24 hours or prolongation of a pre-existing hospitalization should be documented and reported as an SAE unless specifically instructed otherwise in this protocol. There are some hospitalizations that do not require reporting as an SAE.

Treatment within or admission to the following facilities is not considered to meet the criteria of “inpatient hospitalization” (although if any other SAE criteria are met, the event must still be treated as an SAE and immediately reported):

- Emergency department or emergency room
- Outpatient or same-day surgery units
- Observation or short-stay unit
- Rehabilitation facility
- Hospice or skilled nursing facility
- Nursing homes, custodial care, or respite care facility

Hospitalization during the study for a pre-planned surgical or medical procedure (one which was planned prior to entry in the study) does not require reporting as an SAE.

11.3.6 Pre-Existing Medical Conditions

A pre-existing medical condition is one that is present at the start of the study. Such conditions should be recorded on the General Medical History eCRF. A pre-existing medical condition should be recorded as an AE or SAE only if the frequency, severity, or character of the condition worsens during the study. When recording such events on an SAE Report Form and/or AE eCRF, it is important to convey the concept that the pre-existing condition has changed by including applicable descriptors.

CONFIDENTIAL

11.3.7 New Cancers

The development of a new primary cancer should be regarded as an AE and will generally meet at least one of the seriousness criteria (see Section 11.1.2). New primary cancers are those that are not the primary reason for the administration of the study treatment and have developed after the inclusion of the patient into the study. They do not include metastases of the original cancer. Symptoms of metastasis or the metastasis itself should not be reported as an AE/SAE, as they are considered to be disease progression.

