CR = complete response, PR = partial response, SD = stable disease, PD = progressive disease, NE = not evaluable, NA = not applicable (relevant when no target lesions/non-target lesions at baseline).

Special notes on response evaluation

Missing assessments and non-evaluable designation: When no imaging/measurement is done at all at a particular time point, the patient is not evaluable (NE) at that time point. If only a subset of lesion measurements are made at an assessment, usually the case is also considered NE at that time point, unless a convincing argument can be made that the contribution of the individual missing lesion(s) would not change the assigned time point response. This would be most likely to happen in the case of PD.

CONFIDENTIAL

Symptomatic progression: Patients with a global deterioration of health status requiring discontinuation of treatment without objective evidence of PD at that time should be reported as “symptomatic deterioration.” Every effort should be made to document objective progression even after discontinuation of treatment. Symptomatic deterioration is not a descriptor of an objective response: it is a reason for stopping study treatment.

Confirmation of response: Confirmation of response (by repeat scans after 4 weeks or as specified in the protocol) is required for studies in which response rate is the primary endpoint, but is not required in randomized studies or studies with primary survival endpoints (i.e., where response is not a primary endpoint).

References

Eisenhauer et al 2009

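### Section 11.3.7 keeps symptoms of metastasis out of AE and SAE reporting without requiring documented progression, in conflict with 11.3.1, 11.1.5, 11.1.6 and the radiological PFS definition

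*Combined protocol and SAP*

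**What the plan says.** Section 11.3.7, under the heading New Cancers, separates new primary cancers from metastases and then adds: "Symptoms of metastasis or the metastasis itself should not be reported as an AE/SAE, as they are considered to be disease progression". The sentence sets no condition on documentation, seriousness or timing, and it is not limited to new metastases.

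Other sections treat the same subject differently:

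- **11.1.1** defines an AE "without any judgment about causality".
- **11.1.5** requires recording of "All AEs, regardless of seriousness or relationship to patritumab deruxtecan treatment", from the start of treatment to 40 (+7) days after it ends. It also makes clinically significant signs and symptoms reportable as AEs and names no exception for disease symptoms.
- **11.1.6** lists underlying disease among the reasons for answering NO to the causality question.
- **11.3.1** exempts "Progression of malignancy (including fatal outcomes), if documented by use of an appropriate method", and says only that it "should not be reported as an SAE".
- **11.3.6** makes worsening of a condition present at study start an AE or SAE.
- **10.4.2** defines a PFS event as documented radiological progression or death.
- **Appendix B** says of patients who deteriorate without objective progression: "Symptomatic deterioration is not a descriptor of an objective response: it is a reason for stopping study treatment".

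**The concern.** The study enrolls patients with locally advanced or metastatic disease, so many carry lesions from the first day that could plausibly explain dyspnea, cough, nausea, fatigue or pain. Several of these overlap with the drug risks named in 1.2 (nausea, fatigue, decreased appetite) or with the ILD alert symptoms in 6.2.1 (dyspnea, cough).

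Under 11.3.7 the investigator's view of the cause is applied before the event is recorded, and nothing has to support it. Section 10.4.3 assesses safety from the reported incidence of treatment-emergent AEs, in a single-arm, open-label study with no comparator to show what background rate to expect. A rule that filters events before entry therefore changes the main safety output. Two sites following different sections of the same protocol would record the same patient differently.

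**Working it through.** The plan states no figure on this point, so the check sets the rules side by side and then applies them to cases.

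| Section | What is exempt | From AE? | From SAE? | Documentation needed? |
|---|---|---|---|---|
| 11.3.7 | Metastasis and its symptoms | Yes | Yes | No |
| 11.3.1 | Progression of malignancy | No | Yes | Yes |
| 11.1.5 | Nothing | No | No | Not applicable |
| 11.1.6 | Nothing; disease cause is marked unrelated | No | No | Not applicable |
| 11.4.2 | Nothing; qualifying hepatic events are reported even when linked to progression | No | No | Not applicable |

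**Step 1: scope.** 11.3.7 and 11.3.1 differ on both limits, AE versus SAE and documented versus undocumented. A site cannot follow both for a symptom ascribed to a metastasis that has not been shown to progress.

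**Step 2: the stated reason.** 11.3.7 justifies the exemption by calling the symptom disease progression. Under 10.4.2 a symptom alone is not progression. A patient without radiological progression or death has no PFS event and is censored at the last adequate tumor assessment.

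**Step 3: four cases.**

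1. *New lesion on imaging with pain.* Appendix B makes this PD and 10.4.2 counts it. The event is visible in the efficacy data.
2. *Known lung lesions, worsening dyspnea, target lesions stable, no new lesion.* Under 11.1.5 this is an AE. Under 11.3.7, if ascribed to the lung lesions, it is neither an AE nor an SAE, and 10.4.2 records no progression. It appears in neither table.
3. *Global deterioration that stops treatment, no objective PD.* Appendix B has it reported as symptomatic deterioration and asks for continued effort to document progression. If the patient leaves the study before 6 months or has no later scan, 10.4.2 already counts a PFS-6 failure. The record gap is in the AE data.
4. *Raised aminotransferase and bilirubin meeting 11.4.2.* Reportable as an AE and AESI even when related to progression. 11.3.7 does not remove it.

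**Step 4: ILD adjudication.** Section 11.4.1 triggers the data collection for adjudication from AEs reported under ILD query terms, acute respiratory failure or respiratory failure. If such an event is ascribed to lung metastases and not reported, nothing triggers. Section 1.1.3 shows why recording matters. Of 10 patients with potential ILD events requiring adjudication in the earlier study, 7 had events that investigators considered related (6 pneumonitis, 1 ILD). The respiratory failure case was among the other 10 − 7 = 3, and it still entered the adjudication set. Section 11.4.2 overrides disease attribution for hepatic events; 11.4.1 has no equivalent for respiratory events.

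**The case against.** The best defense is that a specific rule governs over a general one: 11.3.7 is a deliberate exception to 11.1.5. The protocol contains other carve-outs, such as progression deaths in 11.3.4 and certain hospitalizations in 11.3.5, and whether to collect disease symptoms as AEs is a legitimate sponsor choice. This answers part of the conflict with 11.1.5, although that section does not point to 11.3.7. It does not answer 11.3.1, which is equally specific and sets different limits, or 10.4.2, which contradicts the reason given.

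Several stronger readings are tempting and do not hold:

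- *That these events never count as progression.* This is true only without radiological PD or death (cases 1 and 3).
- *That Appendix B directly contradicts 11.3.7.* Appendix B classifies tumor response, not AE reporting, and it does require symptomatic deterioration to be reported as such. It undercuts the equation of symptoms with progression, no more.
- *That ILD could go unexamined.* Section 6.2.1 requires ILD to be ruled out when pulmonary symptoms newly appear or worsen, whether or not an AE is entered. The gap is in reporting and adjudication.
- *That the information is lost.* Source records, scans and concomitant medications remain. What is missing is the entry that feeds the tables.

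It is also fair that 11.3.1 prefers one diagnosis to a list of its symptoms, so a rule requiring every symptom of documented progression to be logged separately would create its own friction.

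**Conclusion.** The conflict is real and should be corrected. As written, 11.3.7 removes from the treatment-emergent AE tables any symptom ascribed to a metastasis without radiological PD or death, other than hepatic events caught by 11.4.2. It can also keep respiratory events so ascribed out of ILD adjudication. The effect falls mainly on the safety data; PFS-6 is largely protected by its failure rule.

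No size can be given. A reader might infer one from the earlier study in 1.1.3, where 46/144 (31.9%) had a treatment-emergent SAE and 31/144 (21.5%) a drug-related one, leaving 15/144 (10.4%) with none judged related. The documents do not say how many of those 15 had symptoms ascribed to metastases, or whether that study already excluded such events. Any number of patients derived from that gap would rest on an invented share. The finding rests on the text alone and assumes only that sites apply 11.3.7 as it reads.

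**What to change.** Reconcile 11.3.7 with 11.3.1, 11.1.5, 11.1.6 and 11.3.6:

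1. Only a metastasis or progression documented per Appendix B is exempt as an event. State whether that exemption reaches AEs or SAEs only, and use the same answer in 11.3.1.
2. Clinically significant symptoms without documented progression are recorded as AEs, and as SAEs if a seriousness criterion is met, with attribution to disease entered in the causality field.
3. Add to 11.4.1 a reporting override like the one in 11.4.2, so that potential ILD and respiratory failure events are reported and adjudicated even if attributed to disease.

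The cost is protocol and eCRF-guideline wording, some additional AE entries, and slightly higher all-cause AE and SAE rates. Section 10.4.3 already presents treatment-related AEs separately, so entries marked as due to disease would not raise those summaries.
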